## Interventions.

Nicotine patch. All participants will receive usual psychiatric care plus an offer of the nicotine patch (up to 8 weeks), dosed per package instructions. At the second pre-quit session, participants will be instructed on patch use. The first 4 weeks of patch will be distributed at enrollment and the second 4 weeks will be distributed at the follow-up visit.

Enhanced Usual Care (EUC). Participants in the EUC condition will receive one in-person counseling sessions during the PHP and a second telephone session the week following: the first session will occur prior to the quit day and will focus on establishing a quit plan and instructing the participant on the use of the nicotine patch; the second session will occur prior to quit day and will assess for any difficulties using the nicotine patch. After the second session, participants will be electronically referred to the RI state quitline. This quitline offers an enrollment call and 5 proactive counseling telephone counseling telephone calls to those who enroll. Quitline staff make up to 3 attempts per call to reach users. Total scheduled counseling time offered is 120 minutes. If the participant is unexpectedly discharged before their first counseling visit, the counselor will choose one of the following options in order of preference ((1) complete the second counseling session early but not on the same day as the first counseling session,(2) have the patient return to the partial hospital program location for the first counseling session, (3) complete the counseling session by phone and mail materials distributed during the counseling session).

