ACT Care (AC). Participants in the AC condition will receive one in-person and 6 telephone contacts delivered from an ACT framework. Sessions will last approximately 30 minutes. If the participant is unexpectedly discharged before their first counseling visit, the counselor will choose one of the following options in order of preference ((1) have the patient return to the partial hospital program location for the counseling session, (2) complete the counseling session by phone and mail materials distributed during the counseling session). This intervention is an adaptation of the in-person and telephone protocols developed by consultant [name] to deliver an ACT-based smoking cessation treatment to patients with bipolar disorder. This treatment was found to be feasible to deliver both in person (80% retention, 40% verified abstinent at end of treatment, 90% satisfied with treatment) and by telephone (67% retention, 33% verified abstinence, 100% satisfied with treatment).

The intervention targets the six core processes in ACT: acceptance, cognitive defusion, awareness of the present moment, self as context, defining values, and committed action towards values. In ACT, acceptance means increasing willingness to fully engage in all aspects of experience, as opposed to avoiding unpleasant experiences. Cognitive defusion refers to the separation of oneself from the content of one's thoughts, recognizing that cognition does not necessarily have to drive behavior (i.e., a patient can notice themselves having a thought and choose not to act on it).

Awareness of the present moment means being fully in contact with the present moment rather than dwelling psychologically in the past or the future (e.g., rumination about past failures or worry about future challenges). Self as context refers to the awareness that there is a self, independent of the content of thoughts or experiences that acts as an observer of these events.

Defining values is the process of identifying what is meaningful to individuals. Finally, committed action means making concrete value driven behavior change (as opposed to behavior driven by avoidance). The intervention relies heavily on experiential in-session exercises and metaphors as a means of helping smokers learn *in vivo* to apply ACT principles to the task of quitting smoking.

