### PROTECTION AGAINST RISK:

Minimization of nicotine patch side effects: The nicotine patch is an over the counter medication with few serious side effects. However, participants will be screened for all contraindications to the patch. If a contraindication is present, they must obtain approval from a medical provider before participating. Participants will agree to consult with their outpatient medical providers regarding the safety of using the patch if their medical status changes after the patch is initially provided. Further, study counselors will explain the patch's purpose, application, and side effects, as well as how to use the patch in a manner that minimizes risk.

To minimize skin reactions, participants will be instructed to move the site of patch placement each day and to not repeat site use for at least one week. Patch dose may be adjusted downward if there is significant nausea or other reactions. Participants will be instructed to remove the patch before bed if it significantly interferes with sleep. Participants with severe side effects will be asked to discontinue patch use and contact their primary care provider before resuming.

Minimization of nicotine withdrawal symptoms after quitting: Participants that decide to use the nicotine patch will be told that it will reduce but not entirely eliminate withdrawal symptoms. Participants will be instructed to call their outpatient physician or psychiatrist in the case of severe withdrawal reactions. Withdrawal symptoms typically abate within 1 to 2 weeks of quitting and are not medically dangerous.

Minimization of risk from worsening of depression and emergent suicidality: There is no evidence indicating that participation in this trial will worsen depression or cause suicidality. In fact, other studies have found that quitting smoking is associated with improvements in psychiatric symptoms. However, given that participants will be enrolled during an acute psychiatric episode, it is likely that some participants will experience worsening of depression during this study. A minority may experience episodes of suicidal ideation. Thus, we will monitor and respond to these issues in an ethically sensitive manner.

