As part of the Partial Hospital program, all patients are referred to a psychiatrist and a therapist upon discharge. We will obtain a release to inform these mental health providers that their patient is attempting to quit smoking and could experience symptom exacerbation. Participants will be informed that, in the case of symptom exacerbation, they should: (1) discuss the symptoms with their psychiatrist, therapist and/or primary care provider, (2) page [name], a licensed psychologist ([name], a licensed psychologist, will cover if [name] is not available); or, if they pose an immediate risk to themselves or someone else, (3) call 911 or present to the nearest emergency room.

If a participant reports active suicidality (i.e., any recent suicidal attempts, suicidal gestures, or self-injurious behavior; any current plan or intent to engage in suicidal or self-injurious behavior) to any study staff at any time, the participant will be assessed by [name] or [name], who will respond in an appropriate and ethical manner according to the standards of care for suicide prevention (e.g., referral to immediate emergency psychiatric care if danger to self is imminent).

Minimization of risk of inappropriate psychiatric medication dose upon cessation: Upon enrollment in the study, we will inform the patient's PHP psychiatrist of the patient's planned cessation attempt. A benefit of stopping smoking while in the PHP is that patients meet with their psychiatrists daily while in the program to monitor medication effects and side effects. In addition, we will obtain a release of information from the patients to their outpatient psychiatric provider and primary care provider. Upon enrollment, we will fax these providers a form letter indicating that the patient plans to attempt to stop smoking, their anticipated quit date, that they will be using the nicotine patch, and information on potential medication interactions with tobacco cessation.

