Study Title: Acceptance and Commitment Therapy for Tobacco Cessation Among Psychiatric Partial hospital Patients

NCT#: NCT03911960

Date: July 1st, 2020

Data analysis.

Due to small sample sizes, analyses will be descriptive.

Aim 1. To assess the feasibility of the proposed ACT-based counseling program, we will conduct descriptive statistics on number of patients recruited to the program during the enrollment period compared to number of smokers seen in the PHP during the enrollment period. In addition, we will conduct descriptive statistics on the number of sessions completed per group and rates of completion of the follow-up visit. To assess acceptability of the program, we will report descriptive statistics of responses on the Client Satisfaction Questionnaire in each group. To evaluate the safety of offering a tobacco cessation intervention during a PHP, we will report on the number of participants in the trial who are rehospitalized for a psychiatric reason during the treatment period based on participant self-report at end of treatment. To assess for symptom exacerbation we will report means of psychiatric symptoms by group pre and post intervention among those who completed follow-up.

Aim 2. To evaluate for preliminary evidence of efficacy, we will report abstinence rates by group at end of treatment. Those lost to follow-up will be considered smokers.

Aim 3. To assess for the effect of treatment condition on ACT treatment targets, we will report descriptive statistics of treatment targets before treatment and at follow-up for those who completed the follow-up visit.

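### Completer group means of K6 before and after treatment can hide individual worsening, and with cessation treatment in both arms neither they nor the rehospitalization count can isolate the effect of offering cessation

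*SAP*

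**What the plan says.** SAP Aim 1 handles safety in two adjacent sentences.

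- The first opens with the broad objective, "To evaluate the safety of offering a tobacco cessation intervention during a PHP", and attaches it to the number of trial participants rehospitalized for a psychiatric reason, by self-report at end of treatment. It names no comparator and does not ask for the count by group.
- The second has a narrower purpose: "To assess for symptom exacerbation we will report means of psychiatric symptoms by group pre and post intervention". It is limited to participants who attended follow-up. It sets no threshold for exacerbation, no reference course and no count of individuals who worsen.

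The SAP does not name the symptom scale. The K6 is the only psychiatric symptom scale in Protocol Table 2, where it is taken at enrollment and end of treatment. The Protocol's Measures section puts rehospitalization, symptom exacerbation and the K6 together under safety.

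On entry state, the Protocol (Protection Against Risk) says "given that participants will be enrolled during an acute psychiatric episode, it is likely that some participants will experience worsening of depression". It also says that "patients meet with their psychiatrists daily while in the program to monitor medication effects and side effects".

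On treatment (Protocol, Interventions), "All participants will receive usual psychiatric care plus an offer of the nicotine patch". In enhanced usual care there are two study counseling sessions, after which "participants will be electronically referred to the RI state quitline". On the other side, "Participants in the AC condition will receive one in-person and 6 telephone contacts delivered from an ACT framework".

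**The concern.** Exacerbation happens to individuals, and a group mean is a weak summary of it. If most participants recover from the episode that brought them into the PHP while a few deteriorate, the mean can stay flat or improve. Because only completers count, the mean would look better still if those who deteriorate are the ones who miss follow-up.

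The second difficulty is the comparison. Every participant is offered cessation treatment, so the trial does not show how PHP smokers would fare without the offer. A pre/post change mixes natural course with any effect of the offer, and the rehospitalization count has the same gap. The difference between arms is randomized, but it answers a different question: ACT against enhanced usual care.

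At stake is how the pilot's safety results are read. A drop in mean K6 and a low rehospitalization count could be taken as reassurance about offering cessation during a PHP, which the design cannot give.

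**Working it through.** **Inputs from the documents.** There are 20 participants per group, so 2 × 20 = 40 (Protocol, Sample size). The 80% retention reported by earlier inpatient studies serves as the feasibility benchmark (Protocol, Measures): 0.80 × 40 = 32 completers, or 16 per arm, with 20 − 16 = 4 per arm missing K6 at follow-up. Follow-up is five weeks after visit 2, or later (Protocol, Procedures). There is no stated power or precision figure to reproduce, and no K6 mean, SD or expected course. All K6 inputs below are assumptions.

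**1. What each comparison can identify.** Let g be the natural fall, h the effect of being offered any cessation treatment, and d the extra effect of ACT.

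- Enhanced usual care, observed change: −g + h.
- ACT, observed change: −g + h + d.
- Difference: (−g + h + d) − (−g + h) = d.

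Within an arm, h cannot be separated from g. Between arms, h cancels.

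**2. How far natural course could mask a shared effect (SD units).** Regression to the mean gives a fall of (1 − r) × baseline excess. With an excess of 1 to 2 SD and a test-retest correlation r of 0.5 to 0.8:

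- smallest fall: (1 − 0.8) × 1 = 0.2 SD;
- largest fall: (1 − 0.5) × 2 = 1.0 SD.

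With g = 0.5, a harm of h = 0.3 in both arms shows as −0.5 + 0.3 = −0.2, an apparent improvement. A harm of h = 0.5 shows as no change. With g = 0, h would show in full, so the masking depends on there being some natural fall.

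**3. How many can worsen while the mean stays flat.** If a share p worsens by 1 SD and the rest improve by m, the mean is unchanged when p = m / (1 + m):

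| m (SD) | p |
|---|---|
| 0.3 | 0.3 / 1.3 = 23% |
| 0.5 | 0.5 / 1.5 = 33% |
| 0.8 | 0.8 / 1.8 = 44% |

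**4. How many sit above baseline when the mean falls.** Take individual change as Normal with an SD of 5 points and 32 completers:

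| Mean fall (points) | P(change > 0) | Number of 32 |
|---|---|---|
| 2 | P(Z > 0.4) = 34% | 11 |
| 4 | P(Z > 0.8) = 21% | 7 |
| 6 | P(Z > 1.2) = 12% | 4 |

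This model contains no cessation harm. It shows what a mean conceals, and also that a count of worsened participants will not be zero in a harmless trial.

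**5. Precision of the contrast that is identified.** With 16 completers per arm, a 95% interval for the difference in mean change would have a half-width of 2.04 × √(2/16) = 0.72 SD. With all 20 per arm it would be 2.02 × √(2/20) = 0.64 SD. The SAP plans no such interval; the figures show only how rough the description of ACT against enhanced usual care will be.

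**The case against.** The strongest reply is that this is an openly descriptive 40-person pilot with no test, threshold or decision rule for symptoms, and that neither document announces a finding of no exacerbation. That stands. A reader might infer that the plan is built to declare cessation safe; the text does not say so, and the risk lies in interpretation.

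Other stronger readings also go beyond the documents:

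- **That the K6 means are the plan's test of the safety of offering cessation.** The SAP ties that objective to psychiatric rehospitalization. The limit on attribution applies to both measures, but they should not be merged.
- **That the protocol expects quitting to cause harm.** It ties the likely worsening to the acute episode, and the same paragraph says it knows of no evidence that taking part makes depression worse.
- **That individual deterioration goes unseen.** Serious worsening is followed in several ways: the rehospitalization count, chart review and emergency-visit questions (Measures), assessment of reported suicidality (Protection Against Risk), and adverse event reporting with quarterly review (Data and Safety Monitoring Plan). What lacks a planned count is K6 worsening that falls short of these events.
- **That mean K6 is bound to fall.** A fall is plausible, but it is an inference. The protocol also describes this population as prone to further acute episodes and PHP patients as steadier than inpatients.

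The reply also holds that a worsening count cannot attribute harm to cessation. That is correct. The count is proposed because it describes exacerbation, which a mean does poorly. Splitting it by quit attempt would not help: attempts occur after randomization, worsening may itself prevent one, and the cells would be very small.

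**Conclusion.** The point holds in a limited form, as a cheap improvement. Completer group means are the only planned summary of symptom exacerbation, and they can hide worsening in a minority: between 23% and 44% of participants could worsen by 1 SD with a flat mean if the others improve by 0.3 to 0.8 SD. Because both arms receive cessation treatment, neither the pre/post K6 change nor the rehospitalization count can isolate the effect of offering it; the randomized contrast supports only a rough description of ACT against enhanced usual care. The conclusion about attribution follows from the design alone. The size of any masking rests on assumed K6 values, since the documents give none.

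**What to change.** In SAP Aim 1:

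- Add, by arm, the number of participants with K6 above their baseline, the number worse by a margin fixed in advance, and the number missing K6 at follow-up. The documents offer no basis for a particular margin, so the team should choose and justify one.
- Keep the pre and post means as description, and state that a fall is not evidence of safety because participants enter during a treated acute episode.
- State that the trial has no arm without cessation treatment, and limit the comparative safety conclusion, for both K6 and rehospitalization, to ACT against enhanced usual care. The rehospitalization count should therefore be given by arm.
- Do not split worsening by quit attempt; if such a split is shown, label it descriptive only.

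The cost is SAP wording and one table from data already collected. The downside is small, imprecise counts that will show some worsening even without harm, and a narrower safety claim.
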